6.7. Intervention after the End of the Study

Study intervention will not be made available to participants after conclusion of the study.

7. Discontinuation of Study Intervention and Participant Discontinuation/Withdrawal

7.1. Discontinuation of Study Intervention

In rare instances, it may be necessary for a participant to permanently discontinue IP. If IP is permanently discontinued, the participant may remain in the study (following the SoA, except as noted below) to be evaluated for safety and efficacy.

See the SoA (Section 1.3) for data to be collected at the time of intervention discontinuation for ET procedures and follow-up and for any further evaluations that need to be completed.

Participants who permanently discontinued from IP but remain in the study should complete ET procedures (as indicated in the SoA), then continue to participate in subsequent scheduled visits and assessments, as appropriate. After ET visit, PK assessments should not be collected in participants that have permanently discontinued from IP.

Investigational product may be discontinued for a participant for the following reasons (details given below):

- clinical judgment
- AEs
- by request of the participant or participant's designee (e.g., legal guardian)
- severe noncompliance
- the participant requires an excluded therapeutic agent and temporary discontinuation criteria cannot be met, and
- pacemaker that is not MRI-compatible.

Clinical Judgment

AE or clinically significant laboratory value, ECG result, physical examination finding, MRI finding (such as symptomatic ischemic stroke), C-SSRS result, or vital sign measurement of such severity that, in the opinion of the investigator or Lilly-designated Medical Monitor, continued treatment is not in the best interest of the participant.

Hepatic Event or Liver Test Abnormality

Participants who are discontinued from IP due to a hepatic event or liver test abnormality should have additional hepatic safety data collected via the CRF.

Discontinuation of the IP for abnormal liver tests should be considered by the investigator when a participant meets 1 of the following conditions after consultation with the Lilly-designated Medical Monitor:

- ALT or AST >8x ULN
- ALT or AST >5x ULN for more than 2 weeks
- ALT or AST >3x ULN and TBL >2x ULN or INR >1.5
- ALT or AST >3x ULN with the appearance of fatigue, nausea, vomiting, right upper-quadrant pain or tenderness, fever, rash, and/or eosinophilia (>5%)
- ALP >3x ULN
- ALP >2.5x ULN and TBL >2x ULN

- ALP >2.5x ULN with the appearance of fatigue, nausea, vomiting, right quadrant pain or tenderness, fever, rash, and/or eosinophilia (>5%)

C-SSRS

In addition, IP may be discontinued if participants:

- Answer “yes” to Question 4 or Question 5 on the “Suicidal Ideation” portion of the C-SSRS, or
- Answer “yes” to any of the suicide-related behaviors on the Suicidal Behavior portion of the C-SSRS.

A psychiatrist or appropriately trained professional may assist in the decision to discontinue the participant.

ECG

If a clinically significant finding is identified (including, but not limited to changes from baseline in QT interval corrected using QTcF, PR interval or new onset AV block) after enrollment, the investigator or qualified designee will determine if the participant can continue in the study and if any change in participant management is needed. This review of the ECG printed at the time of collection must be documented. Any new clinically relevant finding should be reported as an AE.

Severe Noncompliance

Severe noncompliance to the study protocol, that results in a safety concern, in the judgment of the investigator, may be reason for discontinuing IP.

Excluded Therapeutic Agent

The participant, for any reason, requires a treatment with an excluded therapeutic agent (Section 6.5) and temporary discontinuation criteria cannot be met (see Section 7.1.1).

Pacemaker that is not MRI-compatible

Participants who require a ferromagnetic implant or insertion of a cardiac pacemaker that is not MRI-compatible will be discontinued from IP and may remain in the study off IP with no further MRIs.

7.1.1. Temporary Discontinuation

Treatment can be temporarily discontinued (examples include short-term treatment using a prohibited drug, uncertain AE, hospitalization). Re-starting investigational product is based on Sponsor and the Principal Investigator's judgment. The maximum permissible treatment suspension is a total of 6 weeks over the duration of the study. Temporary treatment discontinuation and restarting needs to be documented. If temporary discontinuation is due to an AE, it should be reported to the Lilly-designated Medical Monitor.

7.2. Participant Discontinuation/Withdrawal from the Study

A participant may withdraw from the study:

- at any time at his/her own request
- at the request of his/her designee (e.g., legal guardian)

- at the discretion of the investigator for safety, behavioral, compliance, or administrative reasons
- if the participant becomes pregnant during the study
- if the participant enrolls in any other clinical study involving an investigational medicinal product or enrollment in any other type of medical research judged not to be scientifically or medically compatible with this study, and
- if participation in the study needs to be stopped for medical, safety, regulatory, or other reasons consistent with applicable laws, regulations, and GCP.

At the time of discontinuing from the study, if possible, an ET visit should be conducted, as shown in the SoA. See SoA for data to be collected at the time of study discontinuation and follow-up and for any further evaluations that need to be completed. The participant will be permanently discontinued both from the IP and from the study at that time.

If the participant withdraws consent for disclosure of future information, the sponsor may retain and continue to use any data collected before such a withdrawal of consent. If a participant withdraws from the study, he or she may request destruction of any samples taken and not tested, and the investigator must document this in the site study records.

7.2.1. Discontinuation of Inadvertently Enrolled Participants

If the sponsor or investigator identifies a participant who did not meet enrollment criteria and was inadvertently enrolled, then the participant should be discontinued from study treatment. Safety follow-up should be performed as outlined in Section 1.3 (Schedule of Activities), Section 8.2 (Safety Assessments), and Section 8.3 (Adverse Events and Serious Adverse Events, and Product Complaints) of the protocol.

7.3. Lost to Follow-up

A participant will be considered lost to follow-up if he or she repeatedly fails to return for scheduled visits and is unable to be contacted by the study site. Site personnel or designee are expected to make diligent attempts to contact participants who fail to return for a scheduled visit or were otherwise unable to be followed up by the site.

Discontinuation of specific sites or of the study as a whole are handled as part of Appendix 1 (Section 10.1).

8. Study Assessments and Procedures

- Study procedures and their timing are summarized in the SoA. Protocol waivers or exemptions are not allowed.
- Immediate safety concerns should be discussed with the sponsor immediately upon occurrence or awareness to determine if the participant should continue or discontinue study intervention.
- Adherence to the study design requirements, including those specified in the SoA, is essential and required for study conduct.
- All screening evaluations must be completed and reviewed to confirm that potential participants meet all eligibility criteria. The investigator will maintain a screening log to record details of all participants screened and to confirm eligibility or record reasons for screening failure, as applicable.

8.1. Efficacy Assessments

Cognitive and functional testing data will be documented using an eCOA tablet. The audio voice recordings of the rater's questions and the participant's and study partner's responses will also be collected via the eCOA tablet during administration of the cognitive and functional testing for central monitoring of rater scale administration. Cognitive and functional testing for each participant should be performed at approximately the same time on each day, whenever possible, to reduce potential variability.

Note that the CDR should be administered by a different rater than the ADAS-Cog₁₃ and MMSE. The ADCS-ADL should be administered by the same rater as the CDR. Each rater should continue administering the same scale whenever possible to the same participant throughout the study. The PI has the responsibility of selecting the raters who will administer the instruments at the site and ensuring all training requirements have been met by those raters. The CDR rater should be blinded to AEs to avoid bias in the CDR assessment.

When administered, cognitive and functional testing should be performed before medical procedures that could be stressful for the participant (e.g., blood draws). Note that some procedures (e.g., MRI, flortaucipir F18 PET imaging) can be conducted on other days within the visit window.

8.1.1. Primary Efficacy Assessment

The iADRS (Wessels et al. 2015) represents a composite that was developed using both a theory-driven approach (incorporating measures of both cognition and function) and a data-mining approach (identifying the most sensitive combination of scales through analysis of data from the Alzheimer's Disease Neuroimaging Initiative and the EXPEDITION, EXPEDITION2, and EXPEDITION3 studies).

The iADRS is a simple linear combination of scores from 2 well-established, therapeutically sensitive, widely accepted measures in AD, the ADAS-Cog₁₃, and the ADCS-iADL, measuring the core domains of AD. All items of these 2 scales are included without additional weighting of items, yielding face validity and ease of interpretation of the composite relative to its components.

The iADRS score will be derived from the ADAS-Cog₁₃ and the ADCS-iADL. The ADAS-Cog₁₃ and the ADCS-ADL will be the actual scales administered to participants.

8.1.2. Secondary Efficacy Assessments

8.1.2.1. MMSE

The MMSE is a brief instrument used to assess cognitive function in participants (Folstein et al. 1975). The instrument measures orientation, memory, and attention; the ability of the participant to name objects; follow verbal and written commands; write a sentence; and copy figures. The range for the total MMSE score is 0 to 30, with lower scores indicating greater level of impairment.

8.1.2.2. ADAS-Cog₁₃

The ADAS-Cog₁₃ is a rater-administered instrument that was designed to assess the severity of dysfunction in the cognitive and noncognitive behaviors characteristic of persons with AD (Rosen et al. 1984). The ADAS-Cog₁₃ should be administered by the same rater from visit to visit to reduce potential variability.

The cognitive subscale of the ADAS, the ADAS-Cog₁₃, consists of 13 items assessing areas of cognitive function that are the most typically impaired in AD: orientation, verbal memory, language, praxis, delayed free recall, digit cancellation, and maze-completion measures (Mohs et al. 1997). The ADAS-Cog₁₃ scale ranges from 0 to 85, with higher scores indicating greater disease severity.

8.1.2.3. CDR-Sum of Boxes

The CDR-SB is a semi-structured interview performed with the participant and study partner (informant) that integrates domains of cognition and function into a single overall score (Berg et al. 1992; Morris 1993). By assigning a severity score for each of the 6 domains, and then summing each domain, a total score known as “Sum of Boxes” is obtained. Higher scores indicate greater disease severity.

The CDR global ratings, calculated using an algorithm, range from 0 (no dementia) to 3 (severe dementia) while CDR-SB scores, calculated by adding the box scores, range from 0 to 18 (with higher scores indicative of more impairment). The informant is queried about the participant’s memory, orientation, judgment and problem solving, community affairs, home and hobbies, and personal care. The participant’s memory, orientation, judgment, and problem-solving ability are assessed. This scale demonstrates acceptable psychometric characteristics (Coley et al. 2011; Cedarbaum et al. 2013) and has been shown to be sensitive enough to detect disease progression, even in populations with less advanced clinical disease (Williams et al. 2013; Wessels et al. 2015).

The CDR should be administered whenever possible by the same rater from visit to visit to reduce potential variability. The study partner and participant must be interviewed separately. The CDR must always be administered to the study partner first and then to the participant.

8.1.2.4. ADCS-ADL

The ADCS-ADL is a 23-item inventory developed as a rater-administered questionnaire that is to be answered by the participant's study partner (Galasko et al. 1997, 2004). The ADCS-ADL should be administered by the same rater from visit to visit to reduce potential variability.

The ADCS-ADL subset of items (items 6a and 7 to 23) for iADLs will be used as a secondary efficacy measure. The focus in the early symptomatic AD population is on the iADLs rather than the bADLs, which are thought to be affected in more severe stages of the disease. The range for the iADL score is 0 to 59, with lower scores indicating greater disease severity.

For each of the specific items, the study partner is first asked if the participant attempted the ADL during the past 4 weeks. If the participant did attempt the ADL, the study partner is asked to rate the participant's performance level based on a set of performance descriptions. Scores for each item and the overall score for the tool are calculated. The range for the total ADCS-ADL score is 0 to 78, with lower scores indicating greater level of impairment. Separate scores for the bADLs (0 to 19) will also be computed.

8.1.3. Exploratory Assessments

8.1.3.1. Digital Clock Drawing Test

The traditional Clock Drawing Test is a well-established and widely used pen and paper cognitive assessment in which individuals draw the face of a clock showing a specific time on a blank page, then copy a pre-drawn clock. The Digital Clock Drawing Test revises this familiar test by combining digitizing pen technology with novel software to precisely measure nuances in cognitive performance beyond task completion (Souillard-Mandar et al. 2016).

Thus, the innovation offered by this technology is the examination of detailed temporal cognitive processes obtained in real time that cannot be captured using the traditional pen and paper testing format.

8.1.3.2. Digit Symbol Substitution Test

The Digit Symbol-Coding test from the Wechsler Adult Intelligence Scale-IV (Wechsler et al. 2008) engages multiple cognitive abilities, but most notably processing speed. The Digit Symbol-Coding is a paper and pencil test presented on a single sheet of paper that requires a participant to match symbols to numbers according to a key located on the top of the page. The participant copies the symbol into spaces below a row of numbers. The number of correct symbols within the allotted time (120 s) constitutes the score. Maximum coding total raw score is 135 points.

8.2. Safety Assessments

Planned time points for all safety assessments are provided in the SoA (Section 1.3).

8.2.1. Physical Examinations

Physical examinations will be performed as indicated in the SoA (Section 1.3).

The complete physical examination will include assessment of

- general appearance
- skin, head, eyes, and neck
- lymph nodes
- thyroid
- abdomen (bowel sounds, liver, and spleen palpation)
- back (costovertebral angle tenderness), and
- musculoskeletal, cardiovascular, and respiratory systems.

Neurological examinations will be performed as indicated in the SoA (Section 1.3).

The examinations will include a thorough assessment of

- gait
- balance
- coordination
- cranial nerves
- sensory and motor systems, and
- reflexes.

If necessary, given the training of the PI, a neurologist may be consulted in the event of significant new findings.

If a clinically meaningful change in an MRI is noted during the study, an additional full neurological exam should be performed as soon as possible, along with any other medical follow-up deemed necessary by the investigator.

8.2.2. Vital Signs

Vital signs, including temperature, will be measured at visits indicated in the SoA (Section 1.3). Vital signs may be repeated as needed.

8.2.2.1. Blood Pressure

Sitting blood pressure and pulse will be measured after approximately 5 min in the sitting position only, as indicated in the SoA. In addition, orthostatic blood pressure and pulse will be measured supine and standing at designated visits, as detailed in the SoA (Section 1.3).

For orthostatic blood pressure monitoring, participants should be supine for at least 5 min and then stand for at least 3 min prior to taking the respective measurements. If the participant feels unable to stand, only supine vital signs will be recorded.

Unscheduled orthostatic vital signs should be assessed, if possible, during any AE of dizziness or posture-induced symptoms.

8.2.2.2. Height, Weight, and Body Temperature

Height and body weight will be measured. Measurements should be taken, when possible, with the same scale for all measurements. Body mass index will be calculated from the height and body weight.

Temperature will be recorded using an oral or tympanic (or another acceptable route) thermometer.

Any body weight data entered into the CRF will be used for the overall data analysis.

The investigator (or qualified designee) must document his/her review of the ECG printed at the time of collection, the final overread ECG report issued by the central ECG laboratory, and any alert reports.

8.2.4. Clinical Safety Laboratory Assessments

- See Appendix 2 for the list of clinical laboratory tests to be performed and the SoA for the timing and frequency.

- The investigator must review the laboratory report, document this review, and record any clinically relevant changes occurring during the study in the AE section of the case report form. The laboratory reports must be retained with source documents unless a Source Document Agreement or comparable document cites an electronic location that accommodates the expected retention duration. Clinically significant abnormal laboratory findings are those which are not associated with the underlying disease, unless judged by the investigator to be more severe than expected for the participant's condition.
- All laboratory tests with values considered clinically significantly abnormal during participation in the study or within the follow-up period after last dose of IP should be repeated until the values return to normal or baseline or are no longer considered clinically significant by the investigator or Lilly-designated Medical Monitor.
 - If such values do not return to normal/baseline within a period of time judged reasonable by the investigator, the etiology should be identified and the sponsor notified.
 - All protocol-required laboratory assessments, as defined in Appendix 2, must be conducted in accordance with the SoA, standard collection requirements and laboratory manual.
- If laboratory values from non-protocol-specified laboratory assessments performed at the institution's local laboratory require a change in participant management or are considered clinically significant by the investigator (e.g., SAE or AE or dose modification), then report the information as an AE.

With the exception of laboratory test results that may unblind the study, Lilly or its designee will provide the investigator with the results of laboratory tests analyzed by a central vendor, if a central vendor is used for the clinical trial.

8.2.5. Magnetic Resonance Imaging

Magnetic resonance imaging of the brain will be performed according to the SoA (Section 1.3) and as clinically indicated.

This technology will be used to check for evidence of clinically relevant exclusion and safety findings (vMRI will also be used to calculate brain volumes, as noted in Section 9.4.3).

The MRI scans will be reviewed by the investigator or qualified designee for immediate participant management. Any clinically significant findings noted at baseline that result in a diagnosis should be recorded as a preexisting condition or AE. After the MRI scan is read locally, the MRI scans will be sent for analysis to a centralized MRI vendor designated by Lilly. Final MRI eligibility at screening will be based on the centralized MRI read by the vendor, which will be reported to the site.

Specific analyses of the scans, including calculations of brain volumes, will be interpreted by the centralized MRI vendor for data analysis and report writing purposes.

Results of centrally read MRIs regarding participant care/safety will be reported back to sites.

8.2.6. Hepatic Safety Monitoring

Close Hepatic Monitoring

Laboratory tests (Section 10.4), including ALT, AST, ALP, TBL, direct bilirubin, gamma-glutamyl transferase, and creatine kinase, should be repeated within 48 to 72 h to confirm the abnormality and to determine if it is increasing or decreasing, if 1 or more of these conditions occur:

If a participant with baseline results of ...	develops the following elevations:
ALT or AST <1.5x ULN	ALT or AST ≥3x ULN
ALP <1.5x ULN	ALP ≥2x ULN
TBL <1.5x ULN	TBL ≥2x ULN (except for participants with Gilbert's syndrome)
ALT or AST ≥1.5x ULN	ALT or AST ≥2x baseline
ALP ≥1.5x ULN	ALP ≥2x baseline
TBL ≥1.5x ULN	TBL ≥2x baseline (except for participants with Gilbert's syndrome)

Abbreviations: ALP = alkaline phosphatase; ALT = alanine aminotransferase; AST = aspartate aminotransferase; TBL = total bilirubin level; ULN = upper limit of normal.

If the abnormality persists or worsens, clinical and laboratory monitoring, and evaluation for possible causes of abnormal liver tests should be initiated by the investigator in consultation with the Lilly-designated Medical Monitor. At a minimum, this evaluation should include physical examination and a thorough medical history, including symptoms, recent illnesses (e.g., heart failure, systemic infection, hypotension, or seizures), recent travel, history of concomitant medications (including over-the-counter), herbal and dietary supplements, and history of alcohol drinking and other substance abuse.

Initially, monitoring of symptoms and hepatic biochemical tests should be done at a frequency of 1 to 3 times weekly, based on the participant's clinical condition and hepatic biochemical tests. Subsequently, the frequency of monitoring may be lowered to once every 1 to 2 weeks, if the participant's clinical condition and laboratory results stabilize. Monitoring of ALT, AST, ALP, and TBL should continue until levels normalize or return to approximate baseline levels.

Comprehensive Hepatic Evaluation

A comprehensive evaluation should be performed to search for possible causes of liver injury if 1 or more of these conditions occur:

If a participant with baseline results of...	develops the following elevations:
ALT or AST <1.5x ULN	ALT or AST ≥3x ULN with hepatic signs/symptoms*, or ALT or AST ≥5x ULN
ALP <1.5x ULN	ALP ≥3x ULN
TBL <1.5x ULN	TBL ≥2x ULN (except for participants with Gilbert's syndrome)
ALT or AST ≥1.5x ULN	ALT or AST ≥2x baseline with hepatic signs/symptoms*, or ALT or AST ≥3x baseline
ALP ≥1.5x ULN	ALP ≥2x baseline
TBL ≥1.5x ULN	TBL ≥1.5x baseline (except for participants with Gilbert's syndrome)

Abbreviations: ALP = alkaline phosphatase; ALT = alanine aminotransferase; AST = aspartate aminotransferase; TBL = total bilirubin level; ULN = upper limit of normal.

* Hepatic signs/symptoms are severe fatigue, nausea, vomiting, right upper quadrant abdominal pain, fever, rash, and/or eosinophilia >5%.

At a minimum, this evaluation should include physical examination and a thorough medical history, as outlined above, as well as tests for Prothrombin time and INR; tests for viral hepatitis A, B, C, or E; tests for autoimmune hepatitis; and an abdominal imaging study (e.g., ultrasound or computed tomography [CT] scan).

Based on the participant's history and initial results, further testing should be considered in consultation with the Lilly-designated Medical Monitor, including tests for hepatitis D virus, cytomegalovirus, Epstein-Barr virus, acetaminophen levels, acetaminophen protein adducts, urine toxicology screen, Wilson's disease, blood alcohol levels, urinary ethyl glucuronide, and serum phosphatidylethanol. Based on the circumstances and the investigator's assessment of the participant's clinical condition, the investigator should consider referring the participant for a hepatologist or gastroenterologist consultation, magnetic resonance cholangiopancreatography, endoscopic retrograde cholangiopancreatography, cardiac echocardiogram, or a liver biopsy.

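### For raised-baseline bilirubin, Protocol 8.2.6 starts the comprehensive hepatic evaluation at a smaller rise than close monitoring, the only one of six rows in that order

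*Protocol*

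**What the plan says.** Section 8.2.6 of the protocol sets out two levels of response to an abnormal liver test. Each has its own table, split by whether the participant's baseline was below 1.5x ULN or at least 1.5x ULN.

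- **Close Hepatic Monitoring.** When a listed elevation occurs, the liver panel "should be repeated within 48 to 72 h to confirm the abnormality and to determine if it is increasing or decreasing". If the abnormality persists or worsens, the investigator starts clinical and laboratory monitoring, at first 1 to 3 times weekly, and an evaluation for causes that includes at least examination and history. For baseline TBL ≥1.5x ULN the trigger is "TBL ≥2x baseline (except for participants with Gilbert's syndrome", the exception closing there.
- **Comprehensive Hepatic Evaluation.** The text reads "A comprehensive evaluation should be performed to search for possible causes of liver injury if 1 or more of these conditions occur". Its minimum content is examination and history "as outlined above, as well as tests for Prothrombin time and INR; tests for viral hepatitis A, B, C, or E", followed by autoimmune hepatitis tests and abdominal imaging. For baseline TBL ≥1.5x ULN the trigger is "TBL ≥1.5x baseline (except for participants with Gilbert's syndrome", with the same exception.

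Exclusion 31 in Section 5.2 bars screening TBL of 2x ULN or more unless Gilbert criteria are met. A participant without Gilbert's syndrome who screens at 1.5 to <2x ULN is therefore not barred by that criterion.

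**The concern.** The comprehensive level is the heavier of the two. It takes over the history and examination of the first level and adds coagulation, serology and imaging. One would expect the lighter response, a prompt repeat of the test, to start no later than the heavier one. For raised-baseline bilirubin it starts later.

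What is at stake is a narrow safety instruction. When bilirubin rises alone to between 1.5 and 2 times a raised baseline, the site must look for causes of liver injury. The TBL row does not tell it to confirm the value within 48 to 72 h, and so does not open the route to the serial-monitoring schedule. Nothing elsewhere in the protocol or SAP explains this order.

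**Working it through.** **Step 1: compare the rows.** All entries come from the two tables in Section 8.2.6. No published figure has to be reproduced.

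| Baseline group | Close monitoring at | Comprehensive evaluation at | Order |
|---|---|---|---|
| ALT or AST <1.5x ULN | 3x ULN | 5x ULN, or 3x ULN with hepatic signs or symptoms | comprehensive higher (equal with symptoms) |
| ALP <1.5x ULN | 2x ULN | 3x ULN | comprehensive higher |
| TBL <1.5x ULN | 2x ULN | 2x ULN | equal |
| ALT or AST ≥1.5x ULN | 2x baseline | 3x baseline, or 2x baseline with hepatic signs or symptoms | comprehensive higher (equal with symptoms) |
| ALP ≥1.5x ULN | 2x baseline | 2x baseline | equal |
| TBL ≥1.5x ULN | 2x baseline | **1.5x baseline** | **comprehensive lower** |

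The comparator cells read, for instance, "ALT or AST ≥3x baseline" and "ALP ≥2x baseline" in the comprehensive table. For normal-baseline bilirubin both tables give "TBL ≥2x ULN (except for participants with Gilbert's syndrome", again with the exception closing there. Three rows are ordered upwards, two are equal, and one is inverted. The two cells of the inverted row cover the same baseline group with the same Gilbert exemption, so they can be compared directly.

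**Step 2: express the band in multiples of ULN.** Let b be baseline TBL in multiples of ULN. Comprehensive evaluation starts at 1.5 × b and close monitoring at 2 × b, so the band between them is 0.5 × b wide.

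| b | 1.5 × b | 2 × b | Width |
|---|---|---|---|
| 1.5 | 2.25 | 3.0 | 0.75 |
| 1.6 | 2.4 | 3.2 | 0.8 |
| 1.75 | 2.625 | 3.5 | 0.875 |
| 1.9 | 2.85 | 3.8 | 0.95 |
| just under 2 | just under 3 | just under 4 | just under 1 |

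The lowest point of the band is 2.25x ULN. At that level a participant with baseline TBL below 1.5x ULN has met the trigger in both tables, since both stand at 2x ULN.

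**Step 3: what applies inside the band, for an isolated TBL rise.**

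- Comprehensive evaluation: required by the TBL row.
- Repeat within 48 to 72 h: not required by the TBL row.
- Monitoring 1 to 3 times weekly: not reached through the TBL row, because it follows from an abnormality that persists or worsens after that repeat.
- Section 8.2.4: laboratory values judged clinically significant are to be repeated until they normalise or lose significance. This rests on judgement and sets neither a 48 to 72 h limit nor a weekly schedule.

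If ALT, AST or ALP also meets its own row, close monitoring starts through that row and the gap closes.

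**Step 4: does an analysis depend on it?** SAP Section 4.10.4 summarises bilirubin and transaminase categories, and its Hy's Law comparison, at fixed multiples of ULN. None uses the multiples of baseline in Section 8.2.6.

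**The case against.** The strongest reply is that the rows do not conflict. Section 8.2.6 never says that close monitoring must come first. Each table is its own list with its own action, and a site can obey both rows at every bilirubin value. On this view the order is only unusual, and it errs towards more investigation. Much of the supposedly lost follow-up is also covered elsewhere: by Section 8.2.4, by the discretionary unscheduled tests in the Schedule of Activities, and by the test list in Appendix 4 (Section 10.4), which includes total and direct bilirubin and so allows a re-measurement during the work-up.

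Most of this stands. A reader might infer that the two rows are incompatible, or that a rise in the band goes unconfirmed and unmonitored. The documents do not support either inference: both rows can be followed, and a general repeat instruction exists. What remains is that the comprehensive level builds on the lighter one, that no text presents the reversed order as deliberate, and that an early work-up would not by itself explain leaving out the timed repeat.

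Two further inferences should be set aside.

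- A reader might suppose that sites would follow only the first table and not act, or that hepatic case report form data would differ by site. Nothing suggests that a site would ignore an explicit row. Section 8.2.6 does not mention a case report form, Section 7.1 ties extra hepatic data to discontinuation of study drug, and SAP Section 4.10.4 ties the form to meeting criteria for hepatic evaluation. The comprehensive table gives one TBL value for this group.
- A reader might put a number on those affected. If 0.5% to 2% of the 330 participants had such a baseline, that would be 330 × 0.005 = 1.65 to 330 × 0.02 = 6.6, or about 2 to 7. The percentages are assumed, and the count covers baseline status only. Those who then had an isolated rise into the band would be some fraction of it.

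**Conclusion.** The point holds as an ordering error in one row of a safety table in the current protocol text. For baseline TBL ≥1.5x ULN without Gilbert's syndrome, the heavier response triggers at 1.5x baseline and the lighter one at 2x baseline, against the pattern of the other five rows. For an isolated TBL rise between those values, the timed repeat and the schedule that follows from it are not triggered by the TBL row.

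The reach is narrow. It concerns mainly participants screened at 1.5 to <2x ULN. That range is a screening limit: chemistry is drawn again at Visit 2, and Section 9.4.1 by default takes the last value before first dose as baseline, so an individual baseline may fall outside it. The number affected is not given. No efficacy analysis, estimand or SAP hepatic analysis changes. Severity: minor.

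**What to change.** The sponsor should reconcile the two TBL rows for baseline ≥1.5x ULN in Section 8.2.6, so that the close-monitoring and comprehensive levels are consistent with each other, and tell sites the outcome. If the present order is intended, a sentence should say so and state what repeat testing applies between 1.5x and 2x baseline. Which values are right, and in which direction the rows move, is for the sponsor to decide.

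The cost is small: one table cell may be enough and two at most, by site letter or in the next amendment. The Schedule of Activities still has clinical chemistry at Visits 801, 802 and 803, so the correction would have some use during post-treatment follow-up.
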